#### I. Background and Significance

The kinematics of scapholunate interosseous ligament (SLIL) injuries are poorly understood. Some patients are relatively asymptomatic while other patients have pain and difficulty with pushing and loading of the wrist. Even more confounding, some patients with complete injury and dissociation of the scaphoid from the lunate may be symptom free, while some patients with partial injuries describe substantial wrist dysfunction.

The kinematics of the wrist may provide insight into this dysfunction. *In vivo* kinematics of the normal wrist has been studied previously, but few studies have characterized the wrist with a SLIL injury. In addition, there are few studies evaluating validated patient-rated outcomes for patients with SLIL injury. The goal of this study would be to evaluate to what degree kinematic abnormalities affect patient-rated outcomes.

A dual fluoroscopic imaging technique has been used to study the kinematics of various joints and quantify the variations associated with ligament insufficiency or ligament reconstruction. We propose an *in-vivo* study on the wrist of patients with SLIL injury. This technique should identify any changes in carpal kinematics and may be able to be correlated to signs and symptoms of pain and osteoarthritis.

Our technique provides a direct technique for measurement of wrist kinematics. The system is not only a viable solution for the investigation of fully dynamic joint kinematics, but also has a low radiation dosage, is non-invasive, and can be constructed using any pair of readily available fluoroscopes. Thus, the DFIS provides an easy and powerful tool for accurately determining 6DOF positions of healthy, injured, and surgically treated wrists in 3D space.

- (1) Wolfe SW et al. *In vivo* scaphoid, lunate, and capitate kinematics in flexion and extension. *J Hand Surg Am* 2000; 25A : 860-9.
- (2) Crisco JJ et al. *In vivo* radiocarpal kinematics and the dart-thrower's motion. *J Bone Joint Surg* 2005; 87A: 2729- 2739.
- (3) Moritomo H et al. Capitate-based kinematics of the midcarpal joint during wrist radioulnar deviation: An *in vivo* three-dimensional motion analysis. *J Hand Surg* 2004; 29A: 668-675.
- (4) Li G et al. *In vivo* articular cartilage contact kinematics of the knee: an investigation using dual-orthogonal fluoroscopy and magnetic resonance image-based computer models. *Am J Sports Med.* 2005 Jan;33(1):102-7.

## II. Specific aims

This represents a study on subjects with scapholunate interosseous ligament (SLIL) injury and *in-vivo* joint kinematics analysis based on a new three-dimensional imaging method which will integrate images from CT scan and from dual-orthogonal fluoroscopy.

We hypothesize that there is no relationship between *in vivo* kinematic abnormalities and patient-rated outcomes for scapholunate interosseous ligament injuries (SLIL)

Our secondary null hypotheses are that: There are no kinematic differences between subjects with unilateral, symptomatic, full thickness scapholunate ligament tears in comparison to the contralateral wrist without scapholunate ligament injury.

We also aim to answer to the below questions:

- What are baseline validated outcomes for subjects with SLIL injury?
- What are baseline physical measures (range of motion, Jamar Dynamometry)?

## III. Subject selection

In this pilot study, we will recruit 10 subjects with the below inclusion criteria:

### Inclusion Criteria

- Patients with a unilateral full thickness scapholunate ligament tear diagnosed by radiographs or advanced imaging.

### Exclusion Criteria

- Patients < 18 years old
- Patients with partial thickness scapholunate ligament tears
- Patients with radiographic arthrosis
- Patients with prior wrist surgery
- Pregnancy

Subjects will be identified from the clinical practice of [name], [REDACTED], [REDACTED], [REDACTED], and [REDACTED]. Plain radiographs of the interest wrist and contralateral wrist and MRI of the interest wrist will be performed to confirm the diagnosis as a routine practice. Consent procedures are detailed below.

## IV. Subject Enrollment

A total number of 10 subjects will be considered for this pilot study. Post-hoc we will determine if our sample size is sufficient in order to perform a multivariable logistic regression analysis using the rule of thumb to avoid fitting a model with too many degrees of freedom in the modeling process. In case we need to enroll higher number of subjects, we will inform the IRB to get the approval beforehand.

Participation is voluntary. Prospective subjects will be invited in the clinic after being diagnosed and will be provided with a flyer explaining the study. The treating physician will ask the subject's permission to have researchers contact them. A researcher who is IRB approved study staff will contact the subject to confirm eligibility, explain the study, and set up the first study appointment.

At the first study visit, the study will first be explained in detail. After reading the consent form, subjects will be able to ask additional questions. [REDACTED] who is an expert research scientist with more than 9 years of experience in Bioengineering Lab and is an IRB approved study staff will obtain informed consent.

### **Study procedures**

Pregnant or breast-feeding women will be excluded from participation. During each study visit, women of childbearing potential will be questioned and urine tested to determine whether they are possibly pregnant. If found pregnant, they will be disqualified from the study. If a pregnancy test is required, [REDACTED] will confirm the urine test kit results and sign the corresponding pregnancy test form. A credentialed, Massachusetts licensed physician or a licensed radiological technologist will be operating fluoroscopes.

### **V.I. Study visits**

Subjects with a unilateral, full thickness scapholunate ligament tear documented by radiographs of the interest and contralateral wrist, MR arthrogram, or MRI of the interest wrist as well with no history or radiographic evidence of wrist injury will be enrolled. A CT scan of both wrists will be obtained. The contralateral wrist will serve as a matched control.

[figure not shown]
Participation in this study will require two visits at the Massachusetts General Hospital. A research assistant who is IRB approved study staff will contact the subject by telephone and/or email to schedule the visits and will ask the subject whether he/she would prefer to do the CT scan and Fluoroscopy in either one longer session or two separate shorter sessions.

The *first visit* after enrolling in this study will be to undergo a CT scan of both wrists. This visit will last approximately 60 minutes. The subject will lie motionless with outstretched hands on a table that slides into a square donut frame for about 2 minutes. Subjects will complete the PRWE, DASH, and SF-12 questionnaires. Questionnaires will be completed on paper. Range of motion of both wrists will be assessed using a goniometer. Grip force of both wrists will be assessed using Jamar Dynamometer. Pinch force will be assessed for both sides using pinch gauge.

The *second visit* will last approximately 60 minutes. Images of the both wrists will be taken with fluoroscopes, which are able to take digital x-ray pictures. During this visit, the subject will perform fully dynamic activities as described below, while the fluoroscopes take digital x-rays, one wrist at a time:

[REDACTED]

[REDACTED]

Each subject will be given a radiation protection apron, a protective thyroid shield, and protection for genital region. The first and second visits can be done in the same day or 2 separate days, whichever is more convenient for the subject.

The data obtained from these visits will be transferred to a computer and will be used to reconstruct three-dimensional wrist models. It will help researchers better understand the association of small bones in the wrist and whether any changes happen in their related movements after SLIL injury.

The CT scan of the contralateral side is designed to answer research questions. This CT scan is not a substitute for one a doctor would order. However, if we believe that we have found a medical problem in the CT, we will ask a doctor who is trained in the reading of CTs, a radiologist, to help us review the images. If the radiologist thinks that there may be abnormalities in the CT images, we will contact the subject and will help him/her get medical follow-up for the problem.

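### Does the word *symptomatic* in the secondary hypothesis conflict with enrolment criteria that never ask for symptoms?

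*Combined protocol and SAP*

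**What the plan says.** Section III states who is recruited: "we will recruit 10 subjects with the below inclusion criteria". The single inclusion criterion is "Patients with a unilateral full thickness scapholunate ligament tear diagnosed by radiographs or advanced imaging". The exclusions are age under 18, partial tears, radiographic arthrosis, prior wrist surgery and pregnancy. V.I. Study visits restates enrolment as "Subjects with a unilateral, full thickness scapholunate ligament tear documented by radiographs of the interest and contralateral wrist" or by MR arthrogram or MRI, and adds that there be no history or film evidence of wrist injury, without naming the wrist. Neither text mentions symptoms.

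II. Specific aims has two hypotheses. The primary one, that kinematic abnormality and patient-rated outcome are unrelated, has no symptom qualifier. The secondary one, on side-to-side kinematic differences, concerns "subjects with unilateral, symptomatic, full thickness scapholunate ligament tears". The protocol does not define symptomatic.

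I. Background and Significance notes that "some patients with complete injury and dissociation of the scaphoid from the lunate may be symptom free" and sets the aim: "The goal of this study would be to evaluate to what degree kinematic abnormalities affect patient-rated outcomes".

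Breast-feeding women are excluded under Study procedures and again in VI. Risks and Discomforts, but the Section III list names only pregnancy.

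**The concern.** By the protocol's own account, a patient can have a complete tear and no symptoms. Such a patient meets Section III and V.I. but falls outside the population named in the secondary hypothesis. V. Biostatistical Analysis does not say whether that patient's pair of wrists enters the side-to-side comparison.

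Two kinds of harm can be imagined. If someone treated the adjective as an entry screen, the low end of the PRWE and DASH scores would be cut off. A real relationship with kinematics would then be weakened, which favours the stated null. If nobody screens, a few pairs in a sample of 10 might not match the secondary hypothesis, and a decision to keep or drop them could be taken after their kinematics are known. With 10 subjects, each one is 10% of the data.

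Two smaller mismatches point the same way. Section III omits both the injury-free condition in V.I. and the breast-feeding exclusion stated elsewhere.

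**Working it through.** **1. Which texts decide entry.** On symptoms, the statements compare as follows.

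| Place | Function | Symptom condition |
|---|---|---|
| III. Subject selection, with its inclusion and exclusion lists | Who is recruited | None |
| V.I. Study visits | Who is enrolled | None |
| II. Specific aims, primary hypothesis | Question | None |
| II. Specific aims, secondary hypothesis | Question | Symptomatic |

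The two texts that work as screening instructions agree. The adjective is in a hypothesis only, so staff who follow the plan do not screen on symptoms.

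**2. What screening would cost the primary question, if it happened.** The protocol gives no alpha, test, effect size or share of symptom-free patients. Assumptions: n = 10, Pearson correlation, two-sided 5% (critical |r| = 0.632), bivariate normal data, and symptom-free patients forming exactly the lowest fraction p of the outcome. The last assumption removes the most range for a given p.

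With v the variance of a standard normal truncated below its p-quantile, the restricted correlation is ρ√v / √(ρ²v + 1 − ρ²). For p = 0.10, v = 0.712. With ρ = 0.761 this gives 0.761 × 0.844 / √(0.579 × 0.712 + 0.421) = 0.642 / 0.913 = 0.70. The power figures come from simulation with 300,000 runs.

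| Share turned away | r when ρ = 0.761 | Power | Chance that 10 subjects enrolled without a screen include at least one such patient, 1 − (1 − p)^10 |
|---|---|---|---|
| 0% | 0.76 | 80% | 0% |
| 2% | 0.74 | 77% | 18% |
| 5% | 0.73 | 74% | 40% |
| 10% | 0.70 | 69% | 65% |
| 20% | 0.67 | 61% | 89% |
| 30% | 0.64 | 55% | 97% |

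With ρ = 0.60, power is 49% unrestricted and 38%, 32% and 28% at shares of 10%, 20% and 30%.

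The power column applies only if patients are turned away for lack of symptoms. Under Section III and V.I. as written, the 0% row holds for the primary question whatever the share is.

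**3. What open enrolment costs the secondary question.** Assumptions: paired t-test, two-sided 5%, 10 pairs, true difference 0.996 SD (80% power).

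- All pairs kept, symptom-free wrists showing the same difference: power stays at 80%.
- All pairs kept, 1, 2 or 3 symptom-free wrists showing half the difference: the mean retained is (10 − 0.5k)/10 = 0.95, 0.90 or 0.85, and simulated power is 75%, 70% or 64%.
- 1, 2 or 3 pairs dropped: noncentral-t power is 74%, 68% or 60%.

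Under these assumptions, keeping every pair is at least as good as dropping some. It is also the natural reading of V.I., where the contralateral wrist is the matched control for the subjects enrolled.

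**4. The list omissions.** The injury-free condition is an express enrolment condition in V.I. Read literally for the index wrist it would contradict having a tear, so it is presumably aimed at the control wrist. Section III already covers part of this by requiring a unilateral tear and excluding arthrosis and prior surgery. Breast-feeding is excluded in two other places. Neither omission admits anyone whom the protocol as a whole keeps out.

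**The case for a change.** The strongest case for a change is that the discordance between injury and symptoms motivates this study, so symptomatic is not a decorative word. The protocol neither defines it nor says how a symptom-free pair is handled, and in a sample of 10 one such pair matters. Deleting or adding one word costs almost nothing.

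Part of this stands. The wording does not match, and the secondary result will strictly describe a wider group than its hypothesis names.

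The rest is weaker. The documents give no share of symptom-free patients. They do say "Subjects will be identified from the clinical practice of" named clinicians, with radiographs and MRI as routine practice. Patients who reach diagnosis that way have probably presented with complaints, though no criterion guarantees it. The worry about dropping pairs after seeing the data comes from an analysis section that names no test or analysis set. That is a separate and wider matter, and editing one adjective would not cure it.

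Neither repair gains much. Deleting the word alters no enrolment, measurement or analysis. Restricting entry to symptomatic patients would need a screening definition, because the PRWE is first completed at the visit after enrolment, and it would narrow the score range on which the primary question depends.

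**Conclusion.** This is a one-word clerical inconsistency, and no change to the plan is needed. Enrolment is open on symptoms in both texts that govern it, which suits the primary hypothesis and leaves its power untouched. For the secondary hypothesis the effect runs from nil, if the clinic sample has no symptom-free patients or their wrists move alike, to a 5% to 15% smaller mean difference if 1 to 3 of the 10 subjects are symptom free and show half the difference. Those counts and that half are assumptions, as are the test and the effect size.

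A sensible analyst would compare all pairs and report the result for full-thickness tears as enrolled. PRWE and DASH scores are collected from the subjects, so a reader can see how symptomatic the sample was. The conclusion assumes that staff apply Section III together with V.I., Study procedures and VI. as written.

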## **V. Biostatistical Analysis**

A total number of 10 subjects will be considered for this pilot study. Post-hoc we will determine if our sample size is sufficient in order to perform a multivariable logistic regression analysis using the rule of thumb to avoid fitting a model with too many degrees of freedom in the modeling process. In case we need to enroll higher number of subjects, we will inform the IRB to obtain approval prior to proceeding.

Data obtained for statistical analysis will include scanning of each wrist at different positions beside a grip and leaning position. At each respective position, translations, rotations, and gap formation will be measured.

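### For subjects who split the two visits, patient-rated scores and wrist kinematics can be measured on different days with no limit on the gap, which may weaken the association named in the first hypothesis

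*Combined protocol and SAP*

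**What the plan says.** Section II (Specific aims) puts the kinematics-to-outcome question first: "We hypothesize that there is no relationship between" in vivo kinematic abnormalities and patient-rated outcomes. The comparison with the contralateral wrist follows and is labelled secondary. The same section also asks for baseline validated outcomes and baseline physical measures.

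Section V.I (Study visits) assigns the two sides of that first question to different visits:

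- First visit, with the CT of both wrists: "Subjects will complete the PRWE, DASH, and SF-12 questionnaires". Range of motion, grip and pinch are measured here too.
- Second visit, with the fluoroscopes: "During this visit, the subject will perform fully dynamic activities as described below, while the fluoroscopes take digital x-rays, one wrist at a time".

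The spacing is the subject's choice. Staff will "ask the subject whether he/she would prefer to do the CT scan and Fluoroscopy in either one longer session or two separate shorter sessions", and the section later confirms: "The first and second visits can be done in the same day or 2 separate days, whichever is more convenient for the subject". The readable text gives no maximum interval, does not repeat the questionnaires at the second visit, and does not plan to record or adjust for the gap. The redacted lines in this section appear to list the wrist activities, and nothing here depends on them.

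On analysis, section V (Biostatistical Analysis) says "A total number of 10 subjects will be considered for this pilot study" and "Post-hoc we will determine if our sample size is sufficient in order to perform a multivariable logistic regression analysis". It names no correlation test, significance level, power or effect size.

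**The concern.** A study of how abnormal motion relates to symptoms needs both measured on the subject in the same state. The motion data come from fluoroscopy. The CT supplies bone geometry for the models, so having the scores close to the CT does not help this question. What matters is the distance in time between the scores and the fluoroscopy, and the plan leaves that open.

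The subjects are recruited in clinic after diagnosis and have treating physicians. Nothing in the plan requires symptoms to be unchanged between the visits. If they change by different amounts in different people, for reasons unrelated to carpal motion, the visit-one score becomes an imperfect stand-in for the score on the fluoroscopy day. The association would then be diluted, by an amount that varies with each subject's choice of dates. A weak or absent association would be harder to interpret, and scores not collected on the fluoroscopy day cannot be recovered later.

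**Working it through.** **The plan's own figure.** The sample of 10 is given without a power calculation, so there is nothing to reproduce. Everything below is illustrative.

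**Inputs from the documents.** n = 10; scores at the first visit; kinematics at the second; the subject chooses one day or two; no maximum interval.

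**Assumed inputs.** A Pearson correlation tested at two-sided 5%; a true same-day correlation r between kinematics and score; a correlation ρ between a subject's score on the questionnaire day and on the fluoroscopy day; and between-visit change unrelated to kinematics. The value r = 0.77 is used only because it gives about 80% power at n = 10. The range of ρ has no source in the documents.

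**Step 1: attenuation.** If every subject splits the visits, observable r = ρ × r:

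- ρ = 0.95: 0.95 × 0.77 = 0.73
- ρ = 0.90: 0.90 × 0.77 = 0.69
- ρ = 0.80: 0.80 × 0.77 = 0.62

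If half split and half attend on one day (ρ = 1 for them), the average factor is (1 + ρ)/2, that is 0.975, 0.95 and 0.90.

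**Step 2: significance threshold.** With 8 degrees of freedom the critical t is 2.306, so the observed correlation must exceed 2.306/√(2.306² + 8) = 0.63.

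**Step 3: power by simulation, n = 10, true r = 0.77.** With no gap, power is 81.6%.

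| ρ | All split | Half split |
|---|---|---|
| 0.95 | 74% | 78% |
| 0.90 | 67% | 74% |
| 0.80 | 52% (51.5% before rounding) | 67% |

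The columns agree with each other. Half splitting at ρ = 0.90 has the same average factor (0.95) as all splitting at ρ = 0.95, and both give 74%. Half splitting at 0.80 matches all splitting at 0.90, at 67%.

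**Step 4: a less favourable true correlation.** At r = 0.5, power is 33% with no gap. It falls to 26% (ρ = 0.90) or 21% (ρ = 0.80) if all split, and to 29% if half split at ρ = 0.90.

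**Step 5: comparison with sampling error.** For an observed r of 0.5 and n = 10, Fisher's z is atanh(0.5) = 0.549 with standard error 1/√7 = 0.378. The limits are 0.549 ± 1.96 × 0.378 = −0.19 and 1.29, which transform back to a 95% interval of about −0.19 to 0.86. Even at ρ = 0.80 for everyone, attenuation moves r only from 0.50 to 0.40, well inside that interval.

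**The case against.** **The questionnaires are where the aims need them.** A reader might infer that they are attached to the wrong visit and that all the clinical measures should move to the fluoroscopy day. The documents do not support that. Section II asks for baseline outcomes and baseline physical measures, and the first visit after enrolment serves both. Range of motion, grip and pinch are not patient-rated outcomes, so the dilution argument does not reach them. Testing grip and pinch on injured wrists just before imaging that includes grip and leaning positions (section V, Biostatistical Analysis) could affect the motion being measured. Moving everything would also lose baseline data for anyone who attended the CT but not the fluoroscopy. This stands, and the fix respects it.

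**The loss may be small or nil.** Every subject is offered a single session. A shift common to all subjects leaves a correlation unchanged; only subject-specific change dilutes it. The documents give no evidence on symptom change over the gap. A reader might take the fall from 82% to 52% as the expected loss, but it requires every subject to split the visits and the lowest assumed ρ. This stands.

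**The planned analysis is not a correlation.** The only model named is a possible logistic regression. Noise in the score could weaken that association too, but the power figures belong to the Pearson illustration alone.

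**Dilution favours the stated hypothesis.** A reader might infer that the schedule tilts the study toward its hypothesised answer. The next hypothesis is called a secondary null, so the first reads as a conventional null as well, and failing to reject it in a pilot of 10 would not confirm it.

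None of this removes the central fact: the plan allows an unlimited gap between the two measurements it wants to relate, and does not record it.

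**Conclusion.** The point holds as a cheap improvement of minor priority. Followed as written, the plan can produce scores and kinematics from different days for any subject who splits the visits. Subject-specific symptom change over that gap may then weaken the first-stated association. There is no such loss for same-day subjects.

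The size cannot be derived from the documents. The illustrated loss at r = 0.77 is about 4 to 15 percentage points of power if half the subjects split the visits (82% to between 78% and 67%) and 8 to 30 points if all do (82% to between 74% and 52%). It rests on an assumed test, true correlation and between-day stability, and on change unrelated to kinematics. Calling the first-stated hypothesis primary is an inference from its position ahead of one labelled secondary.

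The sample of 10 and the unspecified analysis are larger problems. The timing still deserves attention because correcting it costs little and mistimed scores cannot be repaired afterwards.

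**What to change.** In section V.I, leave the baseline questionnaires, range of motion, grip and pinch at the first visit, and add:

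1. When the two visits fall on different days, the subject repeats the PRWE, DASH and SF-12 on paper on the fluoroscopy day, before imaging.
2. The dates of both visits, and so the interval, are recorded for every subject.

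In section V (Biostatistical Analysis), state that the association between kinematics and patient-rated outcome uses the scores from the fluoroscopy day, and that the first-visit scores answer the baseline-outcomes question. For same-day subjects one set serves both purposes.

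The cost is a few extra minutes at the second visit for subjects who split the visits, plus one more set of the same paper forms to enter. It needs no extra visit, no added radiation and no new instrument.
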